## **7.2 Subgroup analyses**

No subgroup analyses are planned.

## **7.3 Frequency of analyses**

The primary analysis will take place when follow-up is complete for all recruited participants. No formal interim analysis is planned. Safety data will be reported to the Data Monitoring and Safety Committee (DMSC) at least annually, together with any additional analyses the committee request. In these reports the data will be presented by group, but the allocation will remain masked.

Interim analyses will be decided in advance in discussion with the Data Monitoring and Safety Committee (DMSC). There is no intention to compare any outcomes between groups at the end of the internal pilot phase; the only analyses will be descriptive statistics to summarise eligibility and recruitment to decide whether the trial satisfies the progression criteria.

## **7.4 Criteria for the termination of the trial**

The trial may be terminated early by the Trial Steering Committee. A decision to terminate may arise from a recommendation by the DMSC to stop the trial, for example based on *an interim analysis of the data from the trial* or if the results of another study make the completion of the trial unnecessary.

## **7.5 Economic issues**

The within-trial economic evaluation will aim to determine the relative cost-effectiveness of adalimumab compared to usual care. We will carry out the cost-effectiveness analysis largely from the perspective of the UK NHS but will also aim to explore costs to society in the form of productivity cost changes.

Established guidelines will be used for the conduct of the economic evaluation [60]. The main outcome measure for the economic evaluation will be quality adjusted life years (QALYs), estimated using the EuroQol EQ-5D 5L, administered at baseline (start of the TRI; n≈400), at 16

weeks (time of exiting the study because of non-response or randomisation;  $n \approx 400$ ), then at each subsequent visit ( $n \leq 174$ ), i.e. 3-monthly up to 12 months and 4 monthly thereafter). Respondents will be assigned valuations derived from published UK population tariffs [61] and the mean number of QALYs per trial arm and incremental QALYs will be calculated.

For the costing component, resource use data will be collected by adding questions to the trial CRFs. Resource use information will be collected on quantities of drugs of financial significance administered in the two alternative trial arms and resources associated with treating any of these drug side-effects, including hospital admissions and additional outpatient visits and GP visits. We will also collect information on patient employment status during the trial in order to estimate productivity cost changes. Unit costs to be added to the resource use information will be taken from nationally published sources such as the BNF and Emit for drug costs and the NHS Reference Costs for any hospital admissions.

The analysis will calculate the average cost and outcome on a per patient basis and use this information to estimate the incremental cost-effectiveness ratios for the different trial arms will be derived, producing an incremental cost per QALY. Probabilistic sensitivity analysis will be used to demonstrate the impact of the variation around the key parameters in the analysis on the baseline cost-effectiveness results. A key sensitivity analysis will be the cost of adalimumab, where we will explore the use of potentially cheaper biosimilars. Results will be expressed in terms of a cost-effectiveness acceptability curve.

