Exclusion criteria:	Steroid-dependent systemic disease requiring $>5\text{mg/day}$ oral prednisolone, untreated or active tuberculosis, uncontrolled glaucoma, multiple sclerosis, HIV positive, hepatitis B or C, syphilis, Lyme disease, toxoplasmosis chorioretinitis, Behcet's disease, heart failure (NYHA III/IV), cancer diagnosed $<5$ years ago or monitoring of cancer where oncologist has concern about anti-TNF, anti-TNF drug within 90 days, intra or peri-ocular steroids within a specified timeframe, pregnant, allergy or hypersensitivity to adalimumab or any of its excipients, presence of an epiretinal membrane likely to prevent an eye meeting response criterion at 16 weeks of central macular thickness $<320\mu\text{m}$ .
Health technologies	80mg subcutaneous injection of Imraldi™ (licensed biosimilar for adalimumab) at the start of the TRI, then fortnightly 40mg injections starting one week after the initial dose, up to 16 weeks (end of TRI); after randomisation, fortnightly injections of 40mg drug or placebo to the end of the

being assessed:	RCT (for between 12 and 170 weeks, about 3 to 40 months), including repeat TRIs;  On transition to the OLE, participants on drug in the RCT will continue to receive fortnightly injections of 40mg drug, participants on placebo in the RCT will receive no ongoing treatment until the end of the OLE (for up to another 76 weeks, about 18 months). In the event of TF in the OLE, participants will exit the study.
Measurement of outcomes. Primary outcome:	TF, defined as need for >5mg/day oral prednisolone to maintain inactive uveitis (decisions to increase oral prednisolone made by masked clinicians) or treat active disease (see 5.8.1), [1] excluding isolated anterior uveitis and including an increase in cystoid macular oedema (see flow diagram). Clinical TF events will be validated by retinal imaging. Follow-up will be censored when all participants have at least 12 weeks follow-up in the RCT and up to 76 weeks follow-up in the OLE.
Secondary outcomes include:	Patient reported outcomes (visual function [2], generic [3], and symptoms of side effects), BCVA, individual TF components, retinal morphology, adverse events (AEs), changes in employment, NHS resource use and costs.

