### **2.3 Evidence that there is a current need for the trial**

The importance of ANIU in relation to the commissioning brief is evidenced by a response to a Freedom of Information request by the research team before applying for funding (10/08/2016). The response stated that 50% of all individual funding requests (IFRs) to NHS England for biologic therapy for autoimmune disease from 01/04/2013 to 31/03/2016 were for uveitis. Most will have been for anti-TNFalpha drugs such as adalimumab, which is effective for ANIU [1, 4].

Although there were frequent IFRs at the time of designing the study, there was no commissioning policy for adalimumab in England for adults. Adalimumab cost £11,000/year when first licensed [47] but the availability of biosimilars have recently reduced this to about £6,600/year (60%), a significant cost-saving to the public if this therapy is commissioned. The cost of sight loss from any cause in 2008 was £17,549 and the cost of ANIU complications is high [37, 48]. This research is needed to provide evidence that adalimumab is effective as an add-on therapy to existing safe doses of immunosuppression, to identify disease phenotypes which may respond, and to produce commissioning guidelines for this high cost therapy.

Systematic reviews of anti-TNFa drugs conclude that adalimumab is beneficial for ANIU refractory to IMT [49, 50]. There is evidence from studies other than randomised controlled trials of the benefit of anti-TNFa drugs in small numbers of patients with specific ANIU syndromes, e.g. multifocal choroiditis, punctate inner choroidopathy and Birdshot Uveitis [51]. Unlike other rare diseases treated with biologics, there is strong evidence that TNFa is a major therapeutic target, increasing the likelihood of anti TNFa drugs being effective for ANIU [30]. Two recent multicentre randomised controlled trials reported in 2016 that, compared to placebo, adalimumab delays treatment failure (TF) for active and inactive ANIU (respectively, VISUAL 1, hazard ratio (HR)=0.5; 95% CI, 0.36-0.70; p<0.001 and VISUAL II, HR=0.57, 95% CI 0.39-0.84; p=0.004) [1, 4].

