### 5.8.2 Secondary outcomes

Secondary outcomes will include:

- a) Individual TF components, assessed at each trial visit;
- b) Retinal morphology (OCT; macular and retinal nerve fibre layer), assessed at each trial visit;
- c) AEs, assessed at each trial visit;
- d) HRQoL measured using the EQ-5D-5L questionnaire [3][7] at the start of TRI, at 16 weeks immediately before randomisation, then 12-weekly after randomization up to week 48 and 16-weekly thereafter;
- e) Patient-reported symptoms of side-effects at the start of TRI, at 16 weeks (immediately before randomisation), then at each trial visit after randomisation and at any interim attendance prompted by an AE;
- f) Patient-reported visual function [2], at the start of TRI, at 16 weeks immediately before randomisation, 12-weekly up to week 48 and 16 weekly thereafter;
- g) Best corrected visual acuity (BCVA) assessed at each trial visit;
- h) Employment status at the start of TRI, at 16 weeks immediately before randomisation, 12-weekly up to week 48 and 16 weekly thereafter;
- i) Resource use at the start of TRI, at 16 weeks immediately before randomisation, and every 12 weeks (up to week 48) or 16 weeks (after week 48) during follow-up after randomisation.

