### **6.3 Research procedures**

Dedicated uveitis clinics are run in each centre, which will consider all new referrals. Medical and uveitis history will be recorded, screening investigations will be ordered and eligibility will be assessed.

Potentially eligible patients will be consented (to screening and the full study on one consent form) prior to full screening assessments (as per Table 1. Schedule of events during the trial) being done. Patients who are eligible to take part after all required screening assessments are done will be enrolled in the TRI after confirming they are still willing to take part.

Data will be collected on the numbers screened, eligible pre- and post-consent and starting the TRI, including reasons for declining participation. Data will be captured in a purpose-designed secure database, with 'real time' validation, which will be developed by the BTC to support the trial. Resource use data will be collected using bespoke questionnaires and trial case report forms (CRFs).

Participants starting the TRI will be seen at 4 weeks (at hospital), 8 weeks (telephone call review) and 16 weeks (at hospital). This visit frequency approximates usual care, when a patient starts treatment with adalimumab. Study assessments will be completed as per the Schedule of events during the trial (table 1).

At the 16 week visit, if a participant is classified as a responder (see 6.3.1) and agrees to continue in the randomised trial, he/she will be randomised (see 5.7, 5.8.1 and 6.1).

Participants who meet the responder criteria will be randomised into the RCT and will have follow-up visits will be scheduled at 12-weekly intervals up to 48 weeks after randomisation and 16-weekly intervals thereafter, consistent with usual care for patients with ANIU.

If treatment failure is suspected in between 12-weekly follow up visits, an unscheduled treatment failure assessment visit should be conducted to include all follow-up assessments as per the schedule of events. If at an unscheduled visit, TF is NOT confirmed to have occurred the participants will still need to attend the next scheduled visit and all assessments conducted as per protocol.

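### Section 7.5 limits non-drug costing to the treatment of drug side-effects, which is narrower than the NHS perspective it claims and would leave out the non-drug NHS cost of treatment failure if applied as written.

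*Protocol*

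**What the plan says.** Section 7.5 sets the perspective: "We will carry out the cost-effectiveness analysis largely from the perspective of the UK NHS". It then states the content of the costing in one sentence with two parts. The first is drugs: "Resource use information will be collected on quantities of drugs of financial significance administered in the two alternative trial arms". The second is "resources associated with treating any of these drug side-effects, including hospital admissions and additional outpatient visits and GP visits". Employment status is added for productivity costs. Unit costs come from national sources, including "the NHS Reference Costs for any hospital admissions".

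Other sections describe resource use without tying it to side-effects:

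- Section 1.1 names "NHS resource use and costs" as a secondary outcome.
- Section 5.8.2 (item i) gives the timing: "Resource use at the start of TRI, at 16 weeks immediately before randomisation, and every 12 weeks" up to week 48, then every 16 weeks.
- Section 6.3 names the instruments, which are bespoke questionnaires and case report forms (CRFs). Their content is not shown.
- Table 1, item 37, ticks resource use at all RCT and OLE visits, including unscheduled ones.

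On the disease itself, section 2.3 argues for the trial partly because "the cost of ANIU complications is high". Section 6.3 requires that, when failure is suspected between visits, "an unscheduled treatment failure assessment visit should be conducted to include all follow-up assessments".

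**The concern.** In the second part of the 7.5 sentence, admissions, outpatient visits and GP visits appear as examples of resources used to treat side-effects. Nothing in the sentence takes in the same contacts when the cause is the uveitis. An unscheduled TF assessment, its imaging, an ocular procedure or surgery for a complication would therefore not qualify.

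This matters because preventing TF is the effect the trial is designed to detect. A scope that counts the drug and its toxicity, but not the non-drug care that follows failure, counts what adalimumab adds and omits part of what it may save. If adalimumab works, the omission falls more heavily on the placebo arm and pushes the incremental cost, and so the cost per QALY, upward. Longer follow-up does not remove an error of scope, and the planned sensitivity analysis on drug price does not address it. Section 3 presents the trial as a model for a commissioning policy, so the cost per QALY is a main product of the study.

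**Working it through.** **1. Which text governs the scope.** Setting the sections side by side:

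- Section 1.1 gives an outcome label.
- Section 5.8.2 and Table 1 give timing.
- Section 6.3 gives instruments.
- Section 7.5 alone says what the costing covers. Its mention of any hospital admissions concerns the source of unit costs. It does not clearly widen what is collected, and it would reach admissions only, not outpatient TF visits, imaging or procedures.

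**2. The planning rates reproduce.** Inputs from sections 1.1 and 5.9: 27% TF-free at 12 months on placebo, hazard ratio 0.5, 90% power, 5% two-sided, 10% loss.

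- TF-free on adalimumab: 0.27^0.5 = 0.520, matching the stated 52%.
- Freedman events: ((1 + 0.5)/(1 − 0.5))² × (1.960 + 1.282)² = 9 × 10.51 = 94.6, so 95.
- Mean 12-month event probability: (0.730 + 0.480)/2 = 0.605.
- Sample size: 95/0.605 = 157.0, and 157.0/0.9 = 174.4, against the stated 174.

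**3. Difference in first failures.**

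- At 12 months: 0.730 − 0.480 = 0.250 per participant. With 87 per arm this is 87 × 0.730 = 63.5 against 87 × 0.480 = 41.8.
- At 36 months, extending the same constant hazards: (1 − 0.27³) − (1 − 0.27^1.5) = 0.980 − 0.860 = 0.12.

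**4. Possible overstatement in year 1.** If the non-drug NHS cost of a TF, C, were wholly uncosted, incremental cost per participant would be too high by 0.2496 × C. The document gives no C, so the values below are assumptions. The last column compares the result with the annual adalimumab price of about £6,600 in section 2.3.

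| Assumed C | Overstatement | Share of £6,600 |
|---|---|---|
| £250 | £62 | 0.9% |
| £500 | £125 | 1.9% |
| £1,000 | £250 | 3.8% |
| £2,000 | £499 | 7.6% |
| £3,000 | £749 | 11.3% |
| £5,000 | £1,248 | 18.9% |

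**5. What is already in scope.** A first TF leads to a repeat run-in of eight open-label injections (section 5.7). At £6,600 a year and 26 fortnightly doses, that is 8 × £6,600/26 = about £2,030 of drug per repeat run-in. It falls under the drug part of the 7.5 sentence and is not part of C.

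**The case against.** A reader might infer that the costs of flares and TF are not measured at all and that the ICER is therefore biased against adalimumab. The document does not support that.

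- **Data loss is not shown.** Section 7.5 does not use the word only. Resource use is scheduled at every RCT and OLE visit, including the unscheduled visits for suspected TF. The questionnaires and CRFs are not shown and may ask broadly. Under section 5.7, intraocular surgery is reported as an adverse event and extra medication for it goes on the medication CRF.
- **Part of the cost of failure is inside the scope.** The repeat run-in adalimumab counts, as do other costly drugs given after TF. Visits follow usual-care frequency (section 6.11), so a failure found at a scheduled visit needs no extra visit to detect it.
- **The bias is conditional and its size is assumed.** It requires both that the items are left uncosted and that adalimumab reduces TF. The 0.25 is a 12-month count of first failures. It narrows with time, and responders to the repeat run-in switch allocation, so later failures could offset part of it.
- **Detail may sit elsewhere.** A health economics plan may set a wider item list.

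All of this stands as a limit on the claim. It does not remove the point. Section 7.5 is not silent on scope, leaving it to a later plan: it states a scope, and that scope is narrower than the perspective and the outcome it is meant to serve.

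**Conclusion.** The point holds as an inconsistency of scope. Section 7.5 ties non-drug resources to drug side-effects, while it claims a largely NHS perspective and section 1.1 lists NHS resource use and costs without restriction. Following 7.5 literally would leave out the non-drug NHS cost of flares, TF and uveitis complications. If adalimumab also reduces TF, incremental cost and cost per QALY would be too high.

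No corrected ICER can be computed, because the document gives no cost per TF. The 0.25 × C figure rests on the planning survival rates, on C being entirely uncosted, and on first failures in year 1 only. It illustrates direction and order of size and is not an estimate of the final bias.

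**What to change.** Reword section 7.5 so that outpatient, GP and emergency contacts, imaging, procedures and admissions are costed in both arms for any uveitis-related or treatment-related reason, including TF and its complications. Cost unscheduled TF visits, imaging and intraocular procedures from the existing visit, CRF and adverse event records. Confirm that the resource-use questions match the reworded scope. A costing limited to drugs and side-effects can be shown as a sensitivity analysis.

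The cost is a change of wording and some extra costing work. GP, emergency or other-hospital contacts that the existing questions did not capture would be hard to recover once data collection ends on 31 March 2026, so they would need a stated assumption. If the forms are already broad, the change only brings 7.5 into line with sections 1.1 and 5.8.2 and Table 1.

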## **8. Trial management**

University Hospitals Bristol NHS Foundation Trust (UHBW) will act as Sponsor. Responsibility for running the RCT will be delegated via an agreement with the University of Bristol. Agreements between the Sponsor and participating centres will be required, as well as standard site-initiation documents, before recruitment commences. The study will be conducted in accordance with Good Clinical Practice (GCP) guidelines, the European Union Directive 2001/20/EC on clinical trials, the Data Protection Act and the UK Policy Framework for Health and Social Care Research. The trial will be registered on an open access clinical trial database (ISRCTN). Clinical trial documents will be archived and held by the Sponsor for 15 years after study closure in accordance with the standard operating procedures of the Sponsor and in compliance with the principles of GCP.

The study will be managed by the CI, clinical and BTC co-applicants, PPI representative and the trial manager, and fully supported by the wider BTC (a UK Clinical Research Network registered clinical trial unit, Reg. No 11 (registered as the Clinical Trials and Evaluation Unit (CTEU). The CTEU has been assimilated into the BTC). The BTC has an established track record of designing, conducting, managing and reporting multi-centre clinical trials in ophthalmology, including trials of investigational medicinal products (e.g. the IVAN and VICI trials, NIHR refs 07/36/01 and 13/94/15). The BTC has experience in building study database systems and providing randomisation services.

The CI and BTC team will work with the co-applicants to prepare the final protocol, submitting the Ethics/HRA, MHRA and local application packs for each site, preparing trial manuals, providing the randomisation service and designing and implementing the data management system. The CI, BTC team and project Sponsor will endeavour to ensure that the trial runs according to the pre-agreed timetable, recruitment targets are met, the CRFs are completed accurately, complies with relevant ethical and other regulatory standards, and that all aspects of the study are performed to the highest quality. Clinical co-applicants and BTC team members

will also train investigators at participating centres, check that centres are ready to start (“green light”) and monitor their progress during the study. The trial manager will be the contact point to provide support and guidance to the participating centres/specialties throughout the study.

### **8.1 Day-to-day management**

The trial will be managed by a Trial Management Group (TMG), which will meet face-to-face or by teleconference approximately monthly. The TMG will be chaired by a Chief Investigator and will include all members of the named research team (see Chief Investigator & Research Team Contact Details).

An appropriately qualified person by training will be responsible at each site for identifying potential trial participants, seeking informed participant consent, randomising participants, liaising with pharmacy, collecting trial data and ensuring the trial protocol is adhered to.

### **8.2 Monitoring of sites**

#### *8.2.1 Initiation visit*

Before the study commences, training session(s) will be organised by BTC. These sessions will ensure that personnel at each site involved fully understand the protocol, CRFs and the operational requirements of the study.

#### *8.2.2 Site monitoring*

The trial coordinating centre will carry out regular monitoring and audit of compliance of centres with GCP and data collection procedures described in section 0. Monitoring of data collection will be via the study database (checks for data completeness and routine data query review), which will be carried out on a regular basis. The ISF and CRFs will be monitored by site self-completed checklists at least once in the lifecycle of the trial. The TMG will review accumulating data on, including but not limited to, screening, eligibility, recruitment, data completeness, adherence to follow-up, adverse events and protocol deviations in the form of central monitoring reports generated approximately monthly.

### **8.3 Trial Steering Committee and Data Monitoring and Safety Committee**

An independent Trial Steering Committee (TSC) will be established to oversee the conduct of the study. It is anticipated that the TSC will comprise the CI and co-lead investigator, an independent chair and at least two additional independent members, at least one of whom will be a patient/public representative. The TSC will develop terms of reference outlining their responsibilities and operational details. The TSC will meet before recruitment begins and regularly (at intervals to be agreed by the TSC but a minimum of once per year) during the course of the study.

An independent DMSC will be established to review safety data during the course of the study and will advise on interim analyses. The DMSC will develop a charter outlining their responsibilities and operational details. The DMSC will meet (before or jointly with the TSC) before the trial begins and they will meet regularly thereafter (at intervals to be agreed by the DMSC but a minimum of once per year). Stopping rules for the trial will be discussed at the first DMSC meeting, and decisions documented in the DMSC Charter.

